1.3.6 Schedule of Procedures and Assessments

The schedule of procedures and assessments is described in protocol section 7. See Figure 2 for the treatment schema.

Figure 2 Treatment Schema**1.4 Sample Size Calculation**

The Phase 1b will follow the standard 3+3 study design. Three DLs of NT-I7 are planned [DL 1 (480 µg/kg IM Q6W), DL 2 (960 µg/kg IM Q6W), and DL 3 (1200 µg/kg IM Q6W)], and up to 18 subjects will be enrolled.

ORR assessed by RECIST 1.1 and iRECIST will be considered as primary efficacy endpoints in each Phase 2a arm and estimated using exact CIs based on the binomial distribution (Clopper-Pearson intervals) from the evaluable subjects for selected arms. All subjects treated in the study with data available for the calculation of the primary endpoint ORR will be considered evaluable. A test from the Simon minimax design for null hypothesis ORR proportion 4% vs alternative hypothesis 21% in the

arm population will be conducted in selected arms at 1-sided alpha = 0.025 and the p-value reported.

Arms I, II, III, IV, and V of the Phase 2a study stage will follow the Simon's two-stage minimax design. Each arm will enroll 17 evaluable subjects in Stage 1 and, if the Go/No Go criterion is met, an additional 8 evaluable subjects in Stage 2 will be enrolled for a total of 25 evaluable subjects/arm. This will provide an estimated 80% power per selected arm in the Phase 2a stage of the study for the primary hypothesis test using the Simon minimax design. Exact 95% binomial Clopper-Pearson CI estimates of ORR from each arm is planned to support the primary hypothesis tests.

Arms IVa, and Va of the Phase 2a study stage will not follow the Simon's two-stage minimax design.

Enrolment of up to 30 subjects per arm (I, II, III, IV, IVa, V, and Va) is planned to account for non-evaluable subjects and dropouts. Up to 238 subjects (up to 18 subjects in Phase 1b, up to 210 subjects in all arms of Phase 2a, and up to 10 subjects in the Biomarker Cohort) are planned to be enrolled in the study.

It has been reported that approximate 7% of pseudo-progression occurred in pembrolizumab monotherapy in patients with melanoma while comparing ORR assessed by RECIST 1.1 vs iRECIST (Hodi FS, 2016). This study will also explore the rate of pseudo-progression in NT-I7 plus pembrolizumab assessed by iRECIST.

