2. GENERAL STATISTICAL CONSIDERATIONS

2.1 General Methods

Statistical analysis will be performed using SAS® software Version 9.4 or later.

For continuous variables, descriptive statistics will include the number of subjects (n), mean, standard deviation (STD), median, minimum, and maximum. Frequencies and percentages will be displayed for categorical data. Percentages by categories will be based on the number of subjects with no missing data.

The estimated mean and median for a set of values should be calculated to one more decimal place than the raw (observed) data and rounded appropriately. Standard errors (or STDs) should be calculated to two decimal places beyond the raw (observed) data and rounded appropriately. Decimal place for minimum and maximum should be the same as raw (observed) data. Percentage values should be reported with one digit to the right of the decimal point. When numerator value is “0”, it should be displayed as “0”. Further, a maximum of 4 decimal places will be used for all summary statistics unless otherwise specified.

Summaries presented by visit will be based on the scheduled assessments as planned in the protocol. Unscheduled assessments will not be included in the by-visit summary tables,

however, will be included in the listings. The summary tables and listings will be presented as follows:

In Phase 1b: By DL and overall. The DLs are defined as:

- DL 1: NT-I7-480 $\mu\text{g}/\text{kg}$ + pembrolizumab 200mg
- DL 2: NT-I7-960 $\mu\text{g}/\text{kg}$ + pembrolizumab 200mg
- DL 3: NT-I7-1200 $\mu\text{g}/\text{kg}$ + pembrolizumab 200mg

In Phase 2a: By dose expansion cohort defined as follows. All subjects in this phase will receive NT-I7 R2PD + Pembrolizumab 200mg.

- Arm I: CPI treated R/R TNBC
- Arm II: CPI treated R/R NSCLC
- Arm III: CPI treated R/R SCLC
- Arm IV: CPI naïve R/R MSS-CRC
- Arm IVa: CPI naïve R/R MSS-CRC
- Arm V: CPI naïve R/R PC
- Arm Va: CPI naïve R/R PC
- Biomarker Cohort: CPI naïve R/R OC

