3. ANALYSIS SETS

3.1 Safety Analysis Set

The safety analysis set is defined as all subjects who received at least one dose (even partially) of one or both study medications. This analysis set will be used for all safety analysis.

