4.11.2 Adverse Events

AE will be coded using MedDRA version 27.1 and graded using the NCI-CTCAE version 5.0.

A TEAE is any AE that starts on/after the first day of study treatment or that worsens on/after the first day of study treatment, and up to 30 days (90 days for serious adverse events [SAEs]) after the date of last dose of study drugs, or initiation of new anticancer therapy, whichever is earlier.

For the purpose for regulatory reporting, relationships of “definite”, “probable” and “possible” to study drug as assessed by the investigator will be defined as related to study treatment. Missing relationship will not be imputed.

Adverse events of special interest (AESIs) in NT-I7 are defined in protocol section 11.4. Events of clinical interest (ECI) in pembrolizumab are defined in protocol section 11.6.

An overall summary of TEAEs using frequencies and percentages of subjects will be presented based on the following categories:

- TEAEs
- NT-I7-related TEAE
- Pembrolizumab-related TEAE
- Either NT-I7 or pembrolizumab-related TEAE
- TEAEs with Grade 3 or higher
- NT-I7-related TEAE with Grade 3 or higher
- Pembrolizumab-related TEAE with Grade 3 or higher
- Either NT-I7 or pembrolizumab-related TEAE with Grade 3 or higher
- Serious TEAE
- NT-I7-related serious TEAE
- Pembrolizumab-related serious TEAE
- Either NT-I7 or pembrolizumab-related serious TEAE
- TEAEs leading to NT-I7 interrupted/held
- TEAEs leading to NT-I7 dose reduced
- TEAEs leading to NT-I7 permanently withdrawn
- TEAEs leading to pembrolizumab interrupted/held
- TEAEs leading to pembrolizumab permanently withdrawn
- TEAEs leading to discontinuation from the study
- AESI in NT-I7
- ECI in pembrolizumab
- TEAEs considered injection site reaction (ISR)
- TEAEs considered infusion-related reactions (IRR)
- TEAEs leading to death

The above events will be tabulated by SOC and PT. SOC will be sorted by descending frequency and then alphabetically for ties. Within each SOC, PT will also be sorted by descending frequency and then alphabetically for ties, by the overall number of subjects in Phase 1b/Phase 2a total. If a PT is reported more than once for a subject, the subject will only be counted once in the incidence for that PT.

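### A TEAE with blank causality drops out of that drug's related rows without trace, which can understate related rates if blanks remain at database lock

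*SAP*

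**What the plan says.** SAP 4.11.2 (Adverse Events) sets the rule in two sentences. The first says that "relationships of “definite”, “probable” and “possible” to study drug as assessed by the investigator will be defined as related to study treatment". The second says: "Missing relationship will not be imputed".

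The same section then describes the output: "An overall summary of TEAEs using frequencies and percentages of subjects will be presented based on the following categories". Nine of those categories depend on relationship: NT-I7-related, pembrolizumab-related and the combined row ("Either NT-I7 or pembrolizumab-related TEAE"), each for all TEAEs, for Grade 3 or higher and for serious TEAEs. These categories are also tabulated by SOC and PT. Further related-TEAE tables are planned by maximum grade and by decreasing PT frequency. No row is listed for not related or for relationship missing, and no footnote or sensitivity analysis covers blanks.

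Two other provisions bear on the percentages. SAP 3.1 says of the safety analysis set (all subjects with at least one dose of either drug): "This analysis set will be used for all safety analysis". SAP 2.1 says: "Percentages by categories will be based on the number of subjects with no missing data". The SAP does not say which governs the denominator of a related row when causality is blank.

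The protocol's attribution scale (Protocol 11.2) has five levels, from definite to unrelated, and no level for unknown.

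**The concern.** A blank is none of the three values that make an event related. With no imputation, the event cannot enter a related row for that drug. In a table of subject counts, the reader cannot tell it from an event that the investigator judged unrelated.

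This differs from how the SAP treats other missing items. Under SAP 2.8.1, an AE with a wholly missing start date is placed at first dose, or at its end date if that is earlier, so it generally counts as treatment-emergent unless its end date shows otherwise. SAP 2.8.2 promises conservative imputation for other incomplete dates. SAP 4.1 gives discontinuation reasons an explicit missing category. Causality gets neither a conservative rule nor a visible category.

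Each event is reported against two drugs, so one attribution can be blank while the other is filled in. Protocol 8.2 itself says that separating the contributions of the two drugs will be hard. At stake is whether the related-toxicity tables for a new combination can be read at face value in groups of 6 to 30 subjects.

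**Working it through.** The plan states no figure on this point, so there is none to reproduce. The check has two parts.

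**Which rows lose the event**

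| NT-I7 relationship | Pembrolizumab relationship | NT-I7-related row | Pembrolizumab-related row | Either row |
|---|---|---|---|---|
| blank | related | lost | counted | counted |
| blank | not related | lost | not counted, as recorded | lost |
| blank | blank | lost | lost | lost |

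A subject disappears from a row only if no other event already puts that subject there. At PT level the SAP says: "If a PT is reported more than once for a subject, the subject will only be counted once in the incidence for that PT". A blank on a repeat event may therefore change nothing.

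**Size**

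Denominators:
- Phase 2a arm: 30. SAP 1.4 states: "Enrolment of up to 30 subjects per arm (I, II, III, IV, IVa, V, and Va) is planned". The target of 25 per arm refers to evaluable subjects for efficacy and is not the safety denominator.
- Biomarker Cohort: up to 10 (SAP 1.4).
- Phase 1b: up to 6 per dose level, with 6 at 1200 µg/kg (SAP 1.3.1).

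Shift per affected subject = 1/N:
- 1/30 = 3.3 points
- 1/10 = 10 points
- 1/6 = 16.7 points
- over all 210 planned Phase 2a subjects, 1/210 = 0.5 points

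A group that closes with fewer treated subjects has a larger step.

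**Direction**

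Let k be the subjects with a recorded related event, m the subjects whose only candidate related event is blank, and q the share of those m that are truly related. The true rate is (k + qm)/N. Three conventions compare as follows:

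- No imputation, all N in the denominator: rate k/N, bias −qm/N, which is never positive.
- Subjects with a blank dropped from the denominator (one reading of SAP 2.1): rate k/(N − m), bias k/(N − m) − (k + qm)/N.
- Blank counted as related, all N: rate (k + m)/N, bias +(1 − q)m/N, which is never negative.

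The values N = 30, k = 3 and m from 1 to 3 are assumed for illustration, because the documents give no missing rate. Without imputation the reported rate is 3/30 = 10.0%. Counting blanks as related gives 4/30 = 13.3%, 5/30 = 16.7% and 6/30 = 20.0% for m = 1, 2 and 3. For m = 3 the biases in percentage points are:

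| q | No imputation, all N | Blanks dropped from denominator | Blank counted as related |
|---|---|---|---|
| 0 | 0.0 | +1.1 | +10.0 |
| 0.1 | −1.0 | +0.1 | +9.0 |
| 0.25 | −2.5 | −1.4 | +7.5 |
| 0.5 | −5.0 | −3.9 | +5.0 |
| 1 | −10.0 | −8.9 | 0.0 |

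If blanks are dropped from the denominator, the sign changes at q = k/(N − m) = 3/27 = 0.11. The statement that the rate can only be understated therefore holds for the full safety set and not for that reading of SAP 2.1. With m = 0 all three conventions agree.

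**The case against.** The strongest reply is that the SAP has prespecified a rule, the investigator's assessment is its source, and the documents show no blank. Protocol 14 and 14.1 provide for edit checks and require sites to answer safety queries. Protocol 11.3.2 requires attribution for any death within 90 days of the last dose. All-causality TEAE, Grade 3 or higher, serious and fatal rows keep every event, as do the AE and SAE listings. AESIs for NT-I7 are reportable whatever their relationship (Protocol 11.4). Counting blanks as related swaps one convention for another, with bias in the opposite direction. All of this stands, and it limits the size of the point. It does not supply a display for a blank that survives to lock, and the 90-day provision does not cover non-fatal Grade 3 or serious events.

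A reader might infer four stronger claims, which the documents do not support:

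- *Blanks are classed as not related.* The SAP says only that nothing is imputed. The event is missing from the related rows, and no not-related row exists to receive it.
- *Related rates are biased downward.* That needs a blank at lock, on a truly related event, in a subject not already in that row. If SAP 2.1 removes such subjects from the denominator, the direction is not fixed either.
- *Blanks cluster in the last events before death or loss to follow-up.* No passage says so, and the attribution requirement for deaths points the other way.
- *Primary safety results are affected.* The AE endpoint for Phase 1b and the safety endpoint for the Biomarker Cohort are incidence, nature and severity of AEs of any cause (SAP 1.2.1, 1.2.2). DLTs do require relatedness, but they have their own definition and committee review, and Phase 1b is complete with the RP2D chosen.

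**Conclusion.** The point holds as a gap in reporting. As written, a TEAE with blank causality for a drug leaves that drug's related, related Grade 3 or higher and related serious rows without any trace in the tables. It leaves the either-drug row only when the other drug is not recorded as related. On the safety-set denominator, related rates are then unchanged or understated, by up to 3.3 points per affected subject in an arm of 30, 10 points in a cohort of 10 and 16.7 points in a dose level of 6.

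These sizes are conditional. They assume that at least one blank remains at lock and that it is the subject's only qualifying event for that row, and the full shift assumes that the event is truly related. With no blanks the effect is zero. The change is still worth making, because the groups are small, the current rule is the non-conservative one, and the denominator is unsettled between SAP 2.1 and 3.1.

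**What to change.** In SAP 4.11.2, replace the sentence on missing relationship with:

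*A TEAE with missing relationship to a study drug will be counted as related to that drug in summary tables and shown as missing in listings; the number of such events will be footnoted, and percentages will use all subjects in the safety analysis set.*

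The last clause settles the denominator for these rows.

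The cost is one sentence and a footnote. The downside is that related rates will be somewhat overstated if some blank events are truly unrelated, by up to 1/N per subject; the footnote makes this visible. If no blanks remain at lock, no related count changes.

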### 11.3.2. Expedited Reporting Guidelines

Use the study protocol number and the protocol-specific subject ID assigned during study registration on all reports. Progression of the cancer under study is not considered an adverse event unless it results in hospitalization or death.

**Note: A death occurring within 90 days of the last administration of study agent requires both routine and expedited reporting, regardless of causality. Attribution to treatment or other cause must be provided.**

Death due to PD should be reported as **Grade 5 “Malignant neoplasm progression”** to be coded under the system organ class (SOC) “Neoplasms benign, malignant and unspecified (incl cysts and polyps)”. Evidence that the death was a manifestation of underlying disease (e.g., radiological changes suggesting tumor growth or progression; clinical deterioration associated with a disease process) should be submitted.

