### Expedited Reporting Requirements for Adverse Events that Occur on Studies under an IND/IDE within 30 Days of the Last Administration of the Investigational Agent/ Intervention

#### FDA REPORTING REQUIREMENTS FOR SERIOUS ADVERSE EVENTS (21 CFR Part 312)

**NOTE:** Investigators **MUST** immediately (within 24 hours) report ANY Serious Adverse Events, whether or not they are considered related to the investigational agent(s)/intervention (21 Code of Federal Regulations [CFR] 312.64)

An AE is considered serious if it results in **ANY** of the following outcomes:

- 1) Death
- 2) A life-threatening AE
- 3) An AE that results in inpatient hospitalization or prolongation of existing hospitalization for  $\geq 24$  hours
- 4) A persistent or significant incapacity or substantial disruption of the ability to conduct normal life functions
- 5) A congenital anomaly/birth defect.
- 6) Important Medical Events (IME) that may not result in death, be life threatening, or require hospitalization may be considered serious when, based upon medical judgment, they may jeopardize the subject and may require medical or surgical intervention to prevent one of the outcomes listed in this definition. (FDA, 21 CFR 312.32; ICH E2A and ICH E6).

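### The Grade 3+, serious and fatal TEAE rows mix disease progression with other events, and no planned row shows them without progression

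*SAP*

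**What the plan says.** Protocol 11.3.2 sets the recording rule: "Progression of the cancer under study is not considered an adverse event unless it results in hospitalization or death". It adds that "Death due to PD should be reported as Grade 5 “Malignant neoplasm progression", under the neoplasms system organ class. It also says: "A death occurring within 90 days of the last administration of study agent requires both routine and expedited reporting, regardless of causality". The seriousness criteria that follow begin "An AE is considered serious if it results in ANY of the following outcomes", and death is first on the list; inpatient hospitalization is also on it.

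SAP 4.11.2 defines a TEAE as an AE that starts or worsens from the first treatment day "up to 30 days (90 days for serious adverse events [SAEs]) after the date of last dose of study drugs", or until new anticancer therapy if that is earlier. Progression is not excluded. The section then states: "An overall summary of TEAEs using frequencies and percentages of subjects will be presented based on the following categories". Those categories include, for all causes, "TEAEs with Grade 3 or higher", serious TEAEs and "TEAEs leading to death". Drug-related versions are listed for the Grade 3+ and serious rows, but not for the fatal row.

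The same section plans a breakdown of every listed category by system organ class and preferred term. It also plans tables of drug-related TEAEs by maximum CTCAE grade, and listings of all AEs, SAEs and fatal TEAEs.

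**The concern.** Readers take the Grade 3+, serious and fatal rates as the summary of harm. Here each row also counts progression, which PFS already counts as an event (progression deaths count in OS as well).

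Three features of the trial make this matter:

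- There is no control arm, so no background rate can be set against these figures.
- SAP 2.1 presents Phase 2a by arm, and each arm is one tumour type. Differences between arms in these rows can therefore reflect tumour prognosis as well as tolerability.
- Protocol 2.4.1.3 reports two fatal myocarditis events with NT-I7 plus a checkpoint inhibitor and does not rule out a causal role for NT-I7. Fatal toxicity should be easy to read from the main table.

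AE incidence and severity are a Phase 1b primary endpoint and a Biomarker Cohort secondary endpoint, so a clean count has direct use.

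**Working it through.** **Tracing one progression death through the rules**

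1. Protocol 11.3.2: fatal progression is an AE, recorded as Grade 5.
2. The protocol's seriousness criteria: death makes it serious, so it gets the 90-day tail rather than the 30-day one.
3. SAP 4.11.2: if it starts inside the window and before new therapy, it is a TEAE.
4. It is Grade 3 or higher, serious and fatal, so it enters all three rows. Progression that leads only to hospitalization enters the serious row.

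**What the planned tables can recover**

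Let R be the subjects in a row and P those with the progression term. The number with a non-progression event lies between R − P and R; it equals R − P only if no subject has both kinds of event. (A large count for any single other term can raise the lower bound.) Illustration with 30 subjects: R = 18 and P = 6 give 12 to 18 subjects, or 40% to 60%. A hand count from the subject listings would settle it, but no table does. In the fatal row the two nearly separate, if each death carries one fatal term.

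**Illustrative size**

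The plan states no expected rate, so there is no figure to reproduce. Assumed inputs:

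- q, the share of subjects with a progression death in the window: 5% to 40%.
- t, the share with a non-progression event in the row: 20% to 65% (Grade 3+), 10% to 40% (serious), 0% to 8.6% (fatal). The 8.6% is 3 of 35, the fatal AEs in the completed NT-I7 monotherapy study (Protocol 2.4.1.2.2).

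For the Grade 3+ and serious rows, assuming independence: row = 1 − (1 − q)(1 − t), and progression-only share = q(1 − t)/row. For the fatal row, with one cause per death: row = q + t, and share = q/(q + t).

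| Row | t | q | Row rate | Progression-only share |
|---|---|---|---|---|
| Grade 3+ | 65% | 5% | 66.75% | 3% |
| Grade 3+ | 35% | 20% | 48.0% | 27% |
| Grade 3+ | 20% | 40% | 52.0% | 62% |
| Serious | 40% | 5% | 43.0% | 7% |
| Serious | 25% | 20% | 40.0% | 38% |
| Serious | 10% | 40% | 46.0% | 78% |
| Fatal | 8.6% | 5% | 13.6% | 37% |
| Fatal | 2% | 20% | 22.0% | 91% |
| Fatal | 0% | 40% | 40.0% | 100% |

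Progression-only subjects exceed half of the Grade 3+ or serious row when q(1 − t) > t, that is when q > t/(1 − t):

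- Grade 3+: q > 25% at t = 20%; q > 54% at t = 35%; impossible at t = 50% or more.
- Serious: q > 11% at t = 10%; q > 33% at t = 25%.
- Fatal: whenever q > t.

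At q = 20% the added points are q(1 − t):

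- Grade 3+: 0.20 × 0.35 = 7 to 0.20 × 0.80 = 16.
- Serious: 0.20 × 0.60 = 12 to 0.20 × 0.90 = 18.
- Fatal: 20, or 5 of 25 to 6 of 30 subjects.

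Two cautions apply. Progression hospitalizations are not in q, so in that respect the serious-row figures are too low. If subjects who die of progression have other severe events more often than independence implies, the added points shrink.

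**The case against.** The other side has a good case, and much of it stands:

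- **Separation by term.** Every category is tabulated by system organ class and preferred term, and a progression death has its own prescribed term. In the fatal table it should be one line that a reader can set aside.
- **Drug-related deaths are visible.** The drug-related tables by maximum grade show Grade 5 events by term, and all fatal TEAEs are listed. A reader might infer from the missing summary row that drug-related deaths cannot be found. The planned outputs do not support that; the count is only absent from the headline table.
- **Myocarditis.** Protocol 11.4 makes it an event of special interest at any grade, and SAP 4.11.2 gives those events their own row, table and listing.
- **Rarity.** Eligibility requires ECOG 0–1 and a life expectancy of at least 12 weeks, and the window closes at new therapy. In the NT-I7 monotherapy study, none of the three fatal events was termed progression, though that study's recording rule is not given. Against this, subjects are relapsed or refractory, and iRECIST response was 11.1% in Arm IV and 7.7% in Arm V (Protocol 2.3), so most did not respond.
- **All-causality rows are the conservative presentation.** Removing progression relies on an open-label judgement of cause of death. This is a good reason to keep the existing rows.

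What these points do not answer is overlap: in the Grade 3+ and serious rows, subjects with both progression and another event cannot be separated in any planned table. The drug-related rows are no substitute, because they answer a different question and rest on attribution of each event to study drug.

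**Conclusion.** The point holds as a gap in presentation. Progression deaths enter all three all-causality rows, progression hospitalizations enter the serious row, and no row without progression is planned. The fatal row is most exposed.

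A reader might go further and infer that these headline rates largely measure tumour progression. The documents do not support that for the three rows together. It is plausible for the fatal row and depends on assumptions for the serious row. For the Grade 3+ row it is unlikely unless progression deaths are very frequent or other Grade 3+ events are rare. The documents give no progression-death rate and no TEAE rates for the combination, so every percentage above is illustrative.

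Efficacy results, sample size and error rates are unaffected. Dose-limiting toxicity requires at least possible relatedness to study treatment, so the rule for finding the maximum tolerated dose is unaffected too.

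**What to change.** Leave the protocol's reporting rule and the existing all-causality rows as they are. In the SAP 4.11.2 overall summary:

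1. Add parallel Grade 3+, serious and fatal TEAE rows that exclude disease-progression preferred terms. List the terms before database lock: Malignant neoplasm progression and any other progression term used. The protocol prescribes a term only for deaths, so progression hospitalizations may be coded differently.
2. Add a row for fatal TEAEs related to either NT-I7 or pembrolizumab.
3. State that both versions will be reported side by side when safety conclusions are drawn. There is no need to base conclusions on the excluding version alone.

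The cost is four extra rows from data already coded, and slightly longer tables. The excluding version depends on the investigator's attribution of death to progression, which a footnote should say.
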